### 7.2.7 Non-hematologic Toxicity

For other non-hematologic toxicities, dose reductions of capecitabine will be at the discretion of the investigator. Dose modification should be made according to the dose modification table. A maximum of 2 dose reductions are permitted.

## 8.0 ADVERSE EVENTS AND POTENTIAL RISKS

The following is a list of AEs (section 8.1) and the reporting requirements associated with observed AEs (sections 8.3 and 8.4).

The clinical course of each event will be followed until resolution, stabilization, or until it has been determined that the study treatment or participation is not the cause.

Serious adverse events that are still ongoing at the end of the study period will necessitate follow-up to determine the final outcome. Any serious adverse event that occurs after the study period is considered to be possibly related to the study treatment or study participation will be recorded and reported immediately.

### 8.1 CB-839

The most commonly encountered toxicities include fatigue, nausea, vomiting, elevation in liver function tests (including alanine aminotransferase (ALT), aspartate aminotransferase (AST), and alkaline phosphatase), elevation in creatinine, constipation, oral pain and photophobia. These have generally been mild and reversible. Elevation in gamma-glutamyltransferase, bilirubin, anorexia, anemia and dizziness have been observed as adverse events in rare instances (<2%). It should be noted that the rate of GGT elevation is more frequent but these elevations are often considered not clinically significant.

See section 7.1 for management recommendations and dose modifications.

### 8.2 Capecitabine

Known side effects occurring in patients receiving capecitabine include:

Hematologic: anemia, neutropenia, thrombocytopenia

Cardiovascular: edema, venous thrombosis

Constitutional: fatigue, pyrexia, swelling in hands, feet or abdomen, pain, chest pain

Dermatologic: hand-foot syndrome, dermatitis, skin discoloration, alopecia

Gastrointestinal: diarrhea, nausea, vomiting, stomatitis, abdominal pain, gastro-intestinal motility disorder, constipation, taste disturbance, upper GI inflammatory disorders, gastrointestinal hemorrhage, ileus

Hepatic: hyperbilirubinemia

Infections: bacterial or viral

Metabolic: appetite decreased, dehydration

Musculoskeletal: back pain, arthralgia

Neurologic: peripheral sensory neuropathy, headache, dizziness, insomnia

Ocular: eye irritation, visual abnormalities

Psychiatric disorders: mood alteration, depression

Pulmonary: dyspnea, cough, pharyngeal disorder, epistaxis, sore throat

Vascular: venous thrombosis

For a comprehensive list of adverse events related to capecitabine, please refer to the FDA-approved package insert (21). See section 7.2 for management recommendations and dose modifications.

### **8.3 Definitions**

#### **8.3.1 Adverse Event**

An **adverse event** (AE) is any unfavorable or unintended event, physical or psychological, associated with administration of a test article in a research study. The event can include abnormal laboratory findings, symptoms, or disease associated with the investigational agents or procedures associated with the research study. The event does not necessarily have to have a causal relationship with the investigational agents under study, any risk associated with the research, the research intervention, or the research assessments.

Adverse events may be the result of the interventions and interactions used in the research; the collection of identifiable private information in the research; an underlying disease, disorder, or condition of the patient; and/or other circumstances unrelated to the research or any underlying disease, disorder, or condition of the patient.

#### **8.3.2 Serious Adverse Events**

A **serious adverse event** (SAE) is any adverse experience occurring at any dose that results in any of the following outcomes:

- Results in **death**.
- Is a **life-threatening** adverse experience. The term life-threatening in the definition of serious refers to an adverse event in which the patient was at risk of death at the time of the event. It does not refer to an adverse event which hypothetically might have

caused death if it were more severe.

- Requires **inpatient hospitalization or prolongation of existing hospitalization**. Any adverse event leading to hospitalization or prolongation of hospitalization will be considered as Serious, UNLESS at least one of the following expectations is met:
  - The admission results in a hospital stay of less than 24 hours OR
  - The admission is pre-planned (e.g., elective or scheduled surgery arranged prior to the start of the study) OR
  - The admission is not associated with an adverse event (e.g., social hospitalization for purposes of respite care).

However it should be noted that invasive treatment during any hospitalization may fulfill the criteria of “medically important” and as such may be reportable as a serious adverse event dependent on clinical judgment. In addition where local regulatory authorities specifically require a more stringent definition, the local regulation takes precedent.

- Results in **persistent or significant disability/incapacity**. The definition of disability is a substantial disruption of a person’s ability to conduct normal life’s functions.
- Is a **congenital anomaly/birth defect**.
- Is an **important medical event**. Important medical events that may not result death, be life-threatening, or require hospitalization may be considered a serious adverse experience when, based upon appropriate medical judgment, they may jeopardize the patient and may require medical or surgical intervention to prevent one of the outcomes listed in this definition. Examples of such medical events include allergic bronchospasm requiring intensive treatment in an emergency room or at home, blood disease or disorders, or convulsions that do not result in inpatient hospitalization, or the development of drug dependency or drug abuse. The development of a new cancer is always considered an important medical event.
- Clear progression of neoplasia should not be reported as an AE or SAE. Findings that are clearly consistent with the expected progression of the underlying cancer should not be reported as an adverse event, and hospitalizations due to the progression of cancer do not necessarily qualify for an SAE. All deaths should be reported as SAEs regardless of the underlying cause. If there is any uncertainty about a finding being due solely to progression of neoplasia, the finding should be reported as an AE or SAE as appropriate.

### 8.3.3 Other Reportable Information

Certain information, although not considered an SAE, must be recorded, reported, and followed up as indicated for an SAE. This includes:

- A case involving a pregnancy exposure to a test article, unless the product is indicated for use during pregnancy e.g., prenatal vitamins. Information about use in pregnancy encompasses the entire course of pregnancy and delivery and perinatal and neonatal outcomes, even if there were no abnormal findings. If a pregnancy is confirmed, test article must be discontinued immediately. All reports of pregnancy must be followed for information about the course of the pregnancy and delivery, as well as the condition of the newborn. When the newborn is healthy, additional follow-up is not needed. Pregnancies occurring up to 6 months after completion of the study treatment must also be reported to the investigator.

- Overdose (e.g., a dose higher than that indicated in the protocol) with or without an AE.
- Abuse (e.g., use for nonclinical reasons) with or without an AE.
- Inadvertent or accidental exposure with or without an AE.

### 8.3.4 Adverse Event Evaluation

The investigator or designee is responsible for ensuring that all adverse events (both serious and non-serious) observed by the clinical team or reported by the patient which occur after the patient has signed the informed consent are fully recorded in the patient's medical records. Source documentation must be available to support all adverse events.

A laboratory test abnormality considered clinically relevant (e.g., causing the patient to withdraw from the study, requiring treatment or causing apparent clinical manifestations, result in a delay or dose modification of study treatment, or judged relevant by the investigator), should be reported as an adverse event.

The investigator or sub-investigator (treating physician if applicable) will provide the following for all adverse events (both serious and non-serious):

- Event term (as per CTCAE)
- Description of the event
- Date of onset and resolution
- **Expectedness of the toxicity**
- **Grade of toxicity**
- **Attribution of relatedness to the investigational agent- (this must be assigned by an investigator, sub-investigator, or treating physician)**
- Action taken as a result of the event, including but not limited to; no changes, dose interrupted, reduced, discontinued, etc. or action taken with regard to the event, i.e. no action, received medication or other intervention, etc.
- Outcome of event

Descriptions and **grading scales** found in the NCI Common Terminology Criteria for Adverse Events (CTCAE) version 4 will be utilized for AE reporting.

**An expected adverse event** is an event previously known or anticipated to result from participation in the research study or any underlying disease, disorder, or condition of the patient. The event is usually listed in the Investigator Brochure, consent form or research protocol.

**An unexpected adverse event** is an adverse event not previously known or anticipated to result from the research study or any underlying disease, disorder, or condition of the patient.

**Attribution** is the relationship between an adverse event or serious adverse event and the study drug. Attribution will be assigned as follows:

- Definite – The AE is clearly related to the study drug.
- Probable – The AE is likely related to the study drug.
- Possible – The AE may be related to the study drug.

- Unlikely – The AE is doubtfully related to the study drug.
- Unrelated – The AE is clearly NOT related to the study drug.

Attribution should be assigned for individual components of the treatment regimen.

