#### 1.2.2 Clinical Data

A phase I study assessed CB-839 administered as a single agent in patients with metastatic solid tumors (17, 18), cumulative exposure to date is 125 patients (data cut 26 January 2016). Patients received CB-839 according to either a three times daily (TID) dosing schedule or a twice daily

dosing schedule (BID with food) during a 21-day treatment cycle. A standard 3+3 dose escalation strategy was employed assessing dose levels ranging from 100-800 mg TID (n=32), and 600-800 mg BID with food (n=27). Treatment was well tolerated with 16% of patients across all trials experiencing a grade 3/4 treatment related adverse event. One dose limiting toxicity occurred (grade 3 creatinine in a patient with known diabetes). The majority of adverse events were related to asymptomatic, reversible elevations in liver function tests (LFTs). Twice daily dosing with food resulted in a lower frequency (1.5%) of grade 3 treatment-related LFT abnormalities than TID dosing and hence has been selected as the dosing schedule to pursue in subsequent studies (18). Pharmacodynamic analyses (see section 1.2.3) have demonstrated that 600 mg BID results in continuous strong glutaminase inhibition in most patients and is a sufficient dose for further study. Expansion cohorts assessing single agent activity of CB-839 600 mg BID have been enrolled in triple negative breast cancer, KRAS-mutant non-small cell lung cancer, renal cell carcinoma, mesothelioma, fumarate-hydratase (FH)-deficient solid tumors, succinate dehydrogenase (SDH)-deficient GIST, succinate dehydrogenase (SDH)-deficient non-GIST and isocitrate dehydrogenase (IDH)-mutant solid tumors and have confirmed the adverse event profile and recommended phase 2 dose (18). Monotherapy dosing at 800 mg BID has also been shown to be safe and well tolerated and is being further explored in the clinic—this dose could eventually become the preferred recommended phase 2 dose. Two-drug combination studies with CB-839 and either paclitaxel, erlotinib, everolimus or docetaxel are planned.

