### 7.1.3 Abnormal liver function tests (AST, ALT, bilirubin)

Grade	CB-839 Modification
1	No change in dose
2	Reduce CB-839 to the next lower dose level
≥ 3	Hold CB-839 until ≤ Grade 1 and resume at the next lower dose level
≥ 3 after resumption of treatment	Hold CB-839 until ≤ Grade 1 and resume at the next lower dose level

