## **14.3 Analytic Plan for Secondary Objectives**

All toxicities will be summarized as the percentage of patients experiencing each type and grade of event according to dose level. Patients who receive at least one dose of treatment will be included in the analysis.

In the phase I portion of the study, response rate will be summarized using frequencies and proportions by dose level. Response to treatment will be determined using RECIST criteria.

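### Section 14.3 summarises laboratory toxicity by event, not by measured value, so any-grade rates can be biased low; add a worst-grade and shift table

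*Combined protocol and SAP*

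**What the plan says.** Section 8.3.4 sets the rule for when a laboratory finding must be reported as an AE. It begins "A laboratory test abnormality considered clinically relevant (e.g., causing the patient to withdraw from the study, requiring treatment or causing apparent clinical manifestations" and goes on to include findings that "result in a delay or dose modification of study treatment, or judged relevant by the investigator". The general definition in 8.3.1 is broader: "The event can include abnormal laboratory findings, symptoms, or disease associated with the investigational agents".

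The analysis is in 14.3: "All toxicities will be summarized as the percentage of patients experiencing each type and grade of event according to dose level". Its population is every treated patient: "Patients who receive at least one dose of treatment will be included in the analysis". No part of section 14 plans a summary of measured laboratory values, by CTCAE grade or by shift from baseline.

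On the known profile of CB-839, section 1.2.2 reports from the single-agent solid-tumour study: "The majority of adverse events were related to asymptomatic, reversible elevations in liver function tests (LFTs"). Section 8.1 lists ALT, AST, alkaline phosphatase and creatinine elevations among the commonest toxicities.

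The calendars in 11.3 and 11.4 schedule a blood count and a comprehensive panel at screening, cycle 1 days 1, 8 and 15, day 1 of each later cycle, and the 30-day follow-up. The panel includes creatinine, AST, ALT, alkaline phosphatase and total bilirubin.

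**The concern.** The known laboratory signal of CB-839 is largely asymptomatic. Findings of that kind are the least likely to meet a relevance test based on symptoms, treatment or withdrawal. If 14.3 counts only what passes that test, its laboratory rates describe both the drug effect and each investigator's reporting habit.

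The direction of any error is fixed. The denominator is everyone who took a dose, so a patient with an unreported rise is counted as having no event. Omission can only lower the rate. The study is open and single-arm, so no control group shares the same reporting habit.

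What is at stake is the accuracy of the any-grade and grade 1 laboratory rates for the combination. The phase II primary endpoint and the two-stage rule are not affected.

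**Working it through.** The plan states no laboratory toxicity rate, so there is no figure to reproduce. The check sets the reporting trigger in 8.3.4 beside the dose rules, grade by grade.

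- **AST, ALT, bilirubin, grade 2 and above.** Section 7.1.3 requires a CB-839 reduction at grade 2, and a hold followed by a lower dose at grade 3 or above. Either is a dose modification, so 8.3.4 makes the finding reportable even without symptoms. These are captured.
- **AST, ALT, bilirubin, grade 1.** Section 7.1.3 says "No change in dose". The dose trigger does not apply, and without symptoms or treatment only investigator judgement remains.
- **Creatinine, grade 2 and above.** Section 7.1.2 calls for a hold at grade 2 and at grade 3 or 4, which triggers reporting. Section 7.0, however, leaves short interruptions for grade 2 non-hematologic toxicity to the treating physician. The two passages need reconciling. As written, capture is likely at grade 2 and firm above it.
- **Creatinine, grade 1.** Section 7.1.2 has no grade 1 row. Reporting rests on judgement.
- **Alkaline phosphatase, any grade.** The heading of 7.1.2 excludes liver function changes, and 7.1.3 names only AST, ALT and bilirubin. Sections 7.1.4 and 7.2.7 leave dose reductions for other non-hematologic toxicities to the investigator. No automatic dose trigger exists at any grade.
- **Values found after treatment ends.** The 30-day panel falls within the reporting window of 8.5, but no dose action can follow it. Without symptoms or treatment, judgement decides at any grade.

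The consequence for AST, ALT or bilirubin during treatment can be written without assuming any numbers. Let *p* be the true proportion of patients with a rise of any grade, *g* the share of those whose worst grade is 1, and *r* the share of grade 1 patients whose rise is reported.

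- Reported any-grade rate = *p*(1 − *g*) + *p g r*
- Shortfall = *p* − [*p*(1 − *g*) + *p g r*] = *p g*(1 − *r*)
- Rate of grade 2 or higher = *p*(1 − *g*), which does not depend on *r*

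If every grade 1 rise is reported (*r* = 1), the shortfall is zero. As *r* falls towards 0, the shortfall approaches *p g*, the whole grade 1 share. For alkaline phosphatase, where judgement applies at every grade, the shortfall is *p*(1 − *r*), with *p* and *r* now taken over all grades of that analyte. The documents give none of *p*, *g* or *r*, so the shortfall can be bounded but not estimated.

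Baseline is a second reason to use measured values. Section 4.2.6 admits AST and ALT up to 2.5 times the upper limit of normal, so an AE count does not cleanly separate new from pre-existing elevation; a shift table does. Phase II creatinine must be below the upper limit at entry, so any later value above it is new and can be counted directly.

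**The case against.** The strongest reply is that the dose-modification limb of 8.3.4 already does most of the work. That is right for grade 2 or higher AST, ALT and bilirubin, and largely right for creatinine. A reader might infer that clinically important liver and creatinine rises are being missed; for protocol-compliant handling during treatment, the documents do not support that.

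Section 8.3.4 also only says what should be reported, with examples. It forbids nothing, and 8.3.1 allows any abnormal laboratory finding to be an AE. Section 1.2.2 shows asymptomatic liver test rises being reported as AEs in an earlier study. This stands as far as it goes: under-reporting is a risk, not a certainty. But permission to report is not a requirement, and the rate still depends on who is reporting.

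A reader might take the remark in 8.1, "It should be noted that the rate of GGT elevation is more frequent but these elevations are often considered not clinically significant", as proof that the relevance test suppresses rates. It is not. It describes general experience with CB-839, does not say how those events were screened, and concerns an analyte outside this trial's panel.

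Two further points stand. The phase II objectives and endpoints include none for safety, so laboratory toxicity should not be called a main phase II output. And 14.3 does not say in terms that only investigator-reported AEs count; that is the natural reading of a summary by type and grade of event.

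**Conclusion.** The point holds as a cheap improvement to the analysis plan. Any-grade laboratory rates under 14.3 can be biased low because grade 1 rises, alkaline phosphatase at any grade and values found after treatment ends reach the table only through investigator judgement. The size runs from none to most of the grade 1 events, and the documents do not allow a narrower statement. A numerical estimate would need reporting and grade shares that the plan does not supply; any chosen range that left out full reporting would build the shortfall in.

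The conclusion rests on two assumptions: that 14.3 counts reported events, and that the dose actions in 7.1.2 and 7.1.3 are applied as written. Under the second, rates of grade 2 or higher AST, ALT and bilirubin during treatment are unaffected.

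**What to change.** Keep 8.3.4 unchanged for AE and SAE reporting, and add to 14.3:

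> Laboratory toxicity will also be tabulated as worst post-baseline CTCAE v4 grade and as shift from baseline to worst grade. Grades will be computed from all blood count and comprehensive panel values, scheduled and unscheduled, for at least AST, ALT, total bilirubin, alkaline phosphatase, creatinine, hemoglobin, ANC and platelets. Every patient who received at least one dose will be included, whether or not an AE was reported. Laboratory abnormalities reported as AEs will be listed separately.

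This needs no new blood draw and alters no dose or management rule. The cost is one paragraph, one shift table and modest entry of values already measured. How much entry is new cannot be judged, because the electronic case report forms mentioned in 13.1 are not part of the documents. The laboratory rates will look less favourable than those from AE reports alone wherever rises went unreported, and readers should be told which table uses which source.

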## 8.4 SAE Report Form

SAEs will be recorded on the FDA Form 3500A (MedWatch) but should only be reported as instructed below. The electronic FDA SAE reporting forms should not be used.

## 8.5 Reporting Procedures for Serious Adverse Events

For the purposes of safety reporting, all adverse events will be reported that occur on or after the day the first dose of study drug is received through 30 days after the final dose of study drug. Adverse events, both serious and non-serious, and deaths that occur during this period will be recorded in the source documents. All SAEs should be monitored until they are resolved or are clearly determined to be due to a patient's stable or chronic condition or intercurrent illness(es). Related AEs will be followed until resolution to baseline or grade 1 or stabilization.

### 8.5.1 SAE Reporting Requirements

- Participating investigators (all sites) must report all serious adverse events to the Lead Site Principal Investigator (e.g. Sponsor-Investigator) within **24 hours** of discovery or notification of the event. The participating investigator must also provide follow-up information on the SAE until final resolution. All SAEs should be reported to the study principal investigator:

[name]  
[REDACTED]  
[REDACTED]

- The Lead Site Principal Investigator will review the SAE and report the event to the FDA, external collaborator(s), and IRB as applicable. Reporting of SAEs by the PI to the IRB will be conducted in accordance with the standard operational procedures and policies of the IRB and adequate documentation will be maintained to attest to the fact that the IRB was properly notified.
- It is the Sponsor-Investigator's responsibility (e.g. lead site PI) to ensure that ALL serious adverse events that are unexpected and suspected to be related (SUSAR) that occur on the study (e.g. ALL SAEs that occur at each enrolling institution) are reported to all participating sites. **Serious Unexpected and Suspected Adverse Reaction (SUSAR)** means an event which requires expedited reporting to the Regulatory Authority and is *suspected* (by the Sponsor-Investigator) to be related to the Study Drug, is *unexpected* (not listed in the Sponsor-Investigator's Brochure), and is *serious* (as defined in the Protocol section 8.3.2). SUSARs are expedited IND safety reports which are required to be reported to the relevant Regulatory Authorities within 7 days (fatal or life-threatening event) or 15

days (all other serious events), the detail for FDA reporting requirements is given below.

- Safety data will be reported in parallel to Calithera Bioscience's PharmacoVigilance agent according to the Safety Data Exchange Agreement at the following:

US Toll Free [contact]  
eFax forwarded to [[contact]](mailto:[contact])  
Email: [contact]

